Treatment Plan	The study will have three phases: pre-induction, induction and maintenance. Two weeks prior to induction (at week -2), subjects will receive the first intravesical instillation of pembrolizumab. During the 6 week induction phase, intravesical BCG will be administered weekly for a total of 6 doses at the standard dose of 50 mg. Concomitant pembrolizumab will be administered intravesically every two weeks for a total of 3 doses (weeks 0, 2, and 4); the starting dose for the first cohort will be 1 mg/kg. The maintenance phase starts on week 7 and continues up to 1 year (last dose and cystoscopy at week 49). Subjects may remain on maintenance treatment up to week 49 or until progression of disease or intolerable adverse effects. Intravesical BCG and intravesical pembrolizumab will be given every 2 weeks for the first 12 weeks of maintenance therapy (weeks 7, 9, 11, 13, 15, and 17 for a total of 6 maintenance doses) and then every 4 weeks thereafter (weeks 21, 25, 29, 33, 37, 41, 45, 49 for a total of 8 doses). Dose escalation for cohorts will follow a standard 3+3 escalation scheme and the additional dose levels are 1mg/kg, 2mg/kg, 5mg/kg and 10mg/kg. BCG dose will remain constant for all patients on all dose levels. Intrapatient dose escalation is not allowed in this protocol.
Statistical Methodology	This is a phase I dose escalation study using the 3+3 design with 4 doses. The dose escalation scheme and rules for determining the primary outcome, the maximum tolerated dose, are described in Section 4.3. It is expected that up to 24 patients evaluable for dose limiting toxicities will be accrued to the study. This 3+3 design has a 91% chance (49%, 17%) of dose escalating when the true toxicity rate for that dose is 10% (30%, 50%).

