clinical NSCLC growth patterns, effectively normalizing dosing for humans in this model. This analysis led to the conclusion that the lowest dose of pembrolizumab with the potential to be equivalent to 10 mg/kg of pembrolizumab was 1-2 mg/kg. Considering the lack of clinical experience with intravesical administration of pembrolizumab and the need for multiple administrations, the dose 1 mg/kg was selected as the start dose in this study and will be used in first cohort of three evaluable subjects. Additional dose levels will include 2 mg/kg and 10mg/kg (see details of doses escalation on Section 4.3).

Because of uncertainty as to which dose schedule will have the better efficacy and safety profile in patients with BCG-refractory NMIBC, two dosing intervals of pembrolizumab will be utilized in this trial, every 2 weeks during induction therapy until week 17 (first cystoscopy) and every 6 weeks for the remaining period of maintenance phase (weeks 23, 29, 35, 41, 47). The shorter interval during induction therapy is based on the hypothesis that maximizing the PD-1 blockade during the BCG instillation might enhance the anti-tumor effect.

There is a possibility of adding an expansion cohort of up to 10 subjects to further define safety and efficacy of pembrolizumab. This will be determined by Merck after completion of the dose escalation phase.

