2 OBJECTIVES & ENDPOINTS

2.1 Primary Objective & Endpoint

The primary objective of this phase I dose-escalation study will be to determine the maximum tolerated dose (MTD) of the study drug (pembrolizumab) when administered intravesically in combination with BCG in patients with high risk or BCG-refractory non-muscle-invasive bladder cancer (up to the individual maximum tolerated dose of each drug alone). The MTD will be defined as the highest dose that causes dose limiting toxicities (DLTs) in <2 of 6 patients.

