3 PATIENT ELIGIBILITY

The target population for this study is patients with high risk or BCG-refractory non-muscle invasive bladder cancer. This will be a single-center trial conducted in the Northwestern

NU Study Number: NU 15U06
Merck Study Number: 3475-265

Medicine Developmental Therapeutics Institute in conjunction with the Department of Urology of Northwestern University at Northwestern Medicine.

Up to 24 evaluable subjects will be needed for this trial, therefore up to a total of 27 may be enrolled in order to achieve the necessary number of evaluable subjects. BCG-refractory is defined as tumor recurrence within 6 months of receiving at least 2 courses of intravesical BCG (at least 5 or 6 inductions and at least 2 or 3 maintenance doses) or T1 high grade disease at the first evaluation following induction BCG alone (at least 5 or 6 induction doses). Therefore, patients who develop a recurrence of bladder cancer during maintenance treatment period with BCG will be also eligible to the present study. However, patients who were not able to complete prior induction BCG treatment because of intolerable toxicities and developed a recurrence will not be eligible for this trial given increased risk of adverse events with repeated exposure.

On average, 1-2 high risk or BCG-refractory potentially eligible patients are seen per month in the Urology clinic, and it is anticipated that one patient will be accrued every 2-3 months. Potential patients may be referred to the Principal Investigator (PI) at Northwestern University, [name], at [contact]. In addition, the sub-investigators have significant experience and collaborations with nearby university and community urology groups to help provide additional referrals for this high priority study when activated.

Eligibility will be evaluated by the study team according to the following criteria. Eligibility waivers are not permitted. Subjects must meet all of the inclusion and none of the exclusion criteria to be registered to the study. Study treatment may not begin until a subject is registered. Please refer to Section 10.3 for complete instructions regarding registration procedures.

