This phase I study will utilize a 3+3 dose escalation scheme for the study drug pembrolizumab with an initial dose of 1 mg/kg given intravesically to the first cohort of three subjects. Details regarding dose escalation can be found in section 4.3. This study will enroll a maximum of 18 evaluable subjects. Evaluable subjects for toxicity will be those who receive at least one dose of the study drug. Evaluable subjects for response are those who meet the minimum treatment and safety evaluation requirements of the study: i. the subject has received the six doses of BCG and three doses of pembrolizumab planned for the induction phase and has sufficient safety data available to assess the occurrence of dose limiting toxicities; ii. the subject has received at least 1 dose of pembrolizumab out of the total 11 doses planned during the maintenance period.

There is a possibility of adding an expansion cohort of up to 10 subjects to further define safety and efficacy of pembrolizumab. This will be determined by Merck after completion of the dose escalation phase.

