4.3 Dose Escalation Scheme

There will be no dose escalation for BCG (patients on all cohorts will receive the same dose). The table below summarizes the pembrolizumab dose levels; subjects will receive the same dose of pembrolizumab during pre-induction, induction and maintenance phases. No dose reductions are permitted for pembrolizumab. BCG may be reduced for toxicity as described in section 4.4. A standard “3+3” dose escalation design will be utilized. Initially, the study will enroll 3 subjects at the starting dose (level 1), after which enrollment will be temporarily suspended until all 3 patients complete the DLT evaluation period (defined as the 2 week pre-induction phase and the seven weeks of induction phase). Once all 3 subjects complete the DLT period and toxicity data has been reviewed by the Northwestern University Data Monitoring Committee, a decision will be made to proceed with escalation accordingly the rules below.

Table 4-2: Escalation Dose Levels			
Dose Level	Pembrolizumab	BCG	Number of patients
1	1 mg/kg	50mg	3-6
2	2 mg/kg	50mg	3-6
3	5 mg/kg	50mg	3-6
4	10 mg/kg	50mg	3-6

The following rules will be used at each dose level to determine whether or not to proceed to the next dose level:

- If 0 of 3 subjects at a given dose level experience a DLT (defined below), then escalation will proceed to the next dose level.
- If 2 or 3 of 3 subjects at a given dose level experience a DLT, then one of the following must occur:
 - If this happens at level 1, the study will be closed to further accrual and the regimen of pembrolizumab + BCG will be considered too toxic at any dose.
 - If this happens at level 2 or beyond, the previous level will be declared the maximum tolerated dose (MTD).
- If 1 of 3 subjects at a given dose level experiences a DLT, then an additional 3 slots will be added (for a total of 6 patients at that level):
 - If 1 of 6 total experiences a DLT, then escalation will proceed to the next level.
 - If ≥ 2 of 6 total experience a DLT, the previous level will be declared the MTD.

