NOTE: Whichever dose level is declared the MTD must have 6 total subjects treated at that level. For example, if 3 subjects are treated at level 2 and 0 subjects experience DLT, escalation would then proceed to level 3. However, if ≥ 2 subjects at level 3 experience DLT, enrollment to level 2 would need to be re-opened to enroll an additional 3 subjects at that level (with 0 or 1 DLT observed in 6 total subjects) in order to declare level 2 the MTD. If dose level 3 is achieved without MTD-defining DLT, dose level 3 will be considered the recommended phase II dose for future trials.

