9 STATISTICAL CONSIDERATIONS

This is a Phase I dose escalation study using the 3+3 design with 4 doses. The dose escalation scheme and rules for determining the primary outcome, the maximum tolerated dose, are described in Section 4.3. In order to achieve up to 24 evaluable patients for dose limiting toxicity and MTD determination, up to 27 patients may be accrued to the study. This 3+3 design has a 91% chance (49%, 17%) of dose escalating when the true toxicity rate for that dose is 10% (30%, 50%).

To achieve the secondary objectives, the dose limiting toxicities and adverse events will be presented as descriptive frequencies and proportions. Serious adverse events will be summarized by type, frequency, timing, severity and attribution.

NU Study Number: NU 15U06
Merck Study Number: 3475-265

Exploratory objectives (PK, response, progression, immune markers) will be summarized with descriptive statistics due to the anticipated small study sample size. Progression free survival (PFS) and overall survival (OS) will be analyzed using the Kaplan-Meier method. The median PFS and OS estimates will be reported along with confidence intervals.

Progression free survival (PFS) time is calculated as the time that elapses between the initiation of trial therapy and the day of first documented disease progression or death from any cause (whichever is sooner) for all eligible subjects who receive at least one dose of trial therapy. If subsequent anti-cancer therapy is initiated without a preceding disease progression, PFS will be censored at the time of initiation of the subsequent anti-cancer therapy. If disease progression or death from any cause is not observed prior to completion of study participation or initiation of subsequent anti-cancer therapy, the PFS will be censored as the last available disease assessment.

Overall survival (OS) time is calculated as the time that elapses between the initiation of trial therapy and the date of death from any cause, date of completion of study participation, or date the subject is lost to follow up (whichever is sooner) for all eligible subjects who receive at least one dose of trial therapy. If death from any cause is not observed prior to completing study participation, the OS will be censored as the time of the last available documentation of survival status.

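### Section 4 names dose level 3 as the phase II dose and caps the study at 18 evaluable, against a four-level design planned for 24

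*Combined protocol and SAP*

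**What the plan says.** Table 4-2 in Section 4.3 lists four pembrolizumab levels: 1, 2, 5 and 10 mg/kg, with 3 to 6 patients each. Section 4.2, Section 7.1.5, Section 9 and the Study Summary agree on four. The escalation rules apply at every level. A level with 0 of 3 DLTs is passed, and so is one with a single DLT after expansion: "If 1 of 6 total experiences a DLT, then escalation will proceed to the next level". Section 2.1 gives the target: "The MTD will be defined as the highest dose that causes dose limiting toxicities (DLTs) in <2 of 6 patients". The NOTE in Section 4.3 requires six treated subjects at the MTD and then ends: "If dose level 3 is achieved without MTD-defining DLT, dose level 3 will be considered the recommended phase II dose for future trials".

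On sample size, Section 4.1 states: "This study will enroll a maximum of 18 evaluable subjects". Three other places differ:

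- Section 3: "Up to 24 evaluable subjects will be needed for this trial, therefore up to a total of 27 may be enrolled".
- Study Summary, Statistical Methodology: "It is expected that up to 24 patients evaluable for dose limiting toxicities will be accrued to the study".
- Section 9: "In order to achieve up to 24 evaluable patients for dose limiting toxicity and MTD determination, up to 27 patients may be accrued".

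Section 1.3.2, describing the levels above the 1 mg/kg start, says: "Additional dose levels will include 2 mg/kg and 10mg/kg". It omits 5 mg/kg.

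**The concern.** The last sentence of the NOTE reads as a top-of-ladder rule, but level 3 is not the top of this ladder. A trial in which 10 mg/kg clears would report an MTD of 10 mg/kg and, by the NOTE, a recommended phase II dose of 5 mg/kg. No other sentence gives a recommended dose for a cleared level 4. A level 3 passed at 0 of 3 is not expanded if level 4 then clears, so the recommended dose could rest on three patients while six had cleared the higher dose.

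The cap of 18 is a second mismatch. A team that applied it would have to stop some trials before the Section 4.3 rules had run their course, with level 4 unopened or incomplete, or with the six subjects required at the MTD not yet treated.

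**Working it through.** **The plan's own figures.** The chance of passing a level with true DLT rate p is P(0 of 3) + P(1 of 3) × P(0 of the next 3):

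pass(p) = (1−p)³ + 3p(1−p)⁵

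At p = 0.10, 0.30 and 0.50 this gives 0.906, 0.494 and 0.172. The 91%, 49% and 17% in Section 9 therefore reproduce. The maximum evaluable number is levels × 6: 4 × 6 = 24, as Sections 3 and 9 say, and 3 × 6 = 18, as Section 4.1 says.

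**The recommended-dose sentence.** With level 3 at 0 of 3 or 1 of 6 DLTs:

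1. The escalation rules open level 4 (10 mg/kg).
2. If level 4 shows 0 or 1 DLT in six, Section 2.1 makes 10 mg/kg the MTD.
3. The condition in the NOTE was already met at step 1, so its recommended dose is 5 mg/kg.

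On the ladder in Section 1.3.2 (1, 2, 10 mg/kg), level 3 would be 10 mg/kg and the sentence would make sense. The amendment history points the same way: Amendment 1 added 5 mg/kg as a fourth level and raised the evaluable number from 12–18 to 24. That only suggests an origin. The conflict lies in the current body text.

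**How often the two doses differ.** The documents give no DLT rates by dose, so the rates below are assumptions. The two doses differ when levels 1 to 3 are passed and level 4 shows at most 1 DLT in six:

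P(MTD = level 4) = pass(p₁) × pass(p₂) × pass(p₃) × P(Bin(6, p₄) ≤ 1)

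The values of pass(p) are 0.973, 0.906, 0.814 and 0.709 at p = 0.05, 0.10, 0.15 and 0.20.

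| Assumed DLT rates, levels 1–4 | P(levels 1–3 passed) | P(≤1 of 6 at level 4) | P(MTD level 4, NOTE says level 3) |
|---|---|---|---|
| 5% flat | 0.9224 | 0.9672 | 0.892 |
| 10% flat | 0.7440 | 0.8857 | 0.659 |
| 20% flat | 0.3558 | 0.6554 | 0.233 |
| 5/10/15/20% | 0.7178 | 0.6554 | 0.470 |
| 10/15/20/30% | 0.5225 | 0.4202 | 0.220 |

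In the remaining trials that pass level 3, level 4 fails and the MTD is usually level 3, which agrees with the NOTE. The probability that level 3 is passed but the final MTD falls below it (after expansion to six) is 0.0002, 0.0019, 0.0092, 0.0113 and 0.0228, in the order of the table.

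**How often 18 is too few.** Exact enumeration of every path through the four-level 3+3, with six subjects required at the MTD or top level:

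| Assumed DLT rates | P(more than 18 needed) | P(all 24 needed) |
|---|---|---|
| 5% flat | 0.0405 | 0.0019 |
| 10% flat | 0.0902 | 0.0076 |
| 20% flat | 0.0917 | 0.0132 |
| 5/10/15/20% | 0.1000 | 0.0076 |
| 10/15/20/30% | 0.1219 | 0.0147 |

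**The case against.** The strongest reply is that the primary result is untouched. The primary objective is the MTD. A recommended phase II dose is not a listed objective, and the sentence in the NOTE assigns no dose to any patient in this trial and changes no escalation step. A recommended dose below the MTD is also not a contradiction in itself. Section 1.3.2 reports modelling in which 1–2 mg/kg might be equivalent to 10 mg/kg, so a lower dose is not implausible. The percentages above are probabilities under invented rates; they show how often the wording matters, not patient harm. The 18 is one outlier against several statements of 24, and in most trials it would not bind.

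Much of this stands. The MTD is defined, the rates are assumptions, and the cap is the lesser problem. Agreement at level 3 when level 4 fails is also not complete. Among trials that pass level 3 and fail level 4, the MTD falls below level 3 in up to about 7.5% (at flat 20%: 0.0092 / (0.3558 − 0.2332) = 0.075).

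What does not stand is the deliberate-choice reading. No text ties level 3 to a reason. The modelling in Section 1.3.2 points to 1–2 mg/kg, not 5, and Section 1.3.1 says the MTD is what later trials will be designed on. Nor can the 18 be read as applying to response only: the sentence carries no such qualifier, and the next one defines evaluability for toxicity.

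**Conclusion.** The concern holds. Two operative sentences in Section 4 do not fit the four-level design that the rest of the protocol describes. The recommended-dose sentence matters more: if 10 mg/kg clears, the dose handed to phase II is half the MTD, without a stated reason. Across the five assumed DLT profiles this happens in 22% to 89% of trials, most often when the drug is well tolerated. The cap of 18 is short by 6 of 24 and would bind in about 4% to 12% of trials.

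The structural conflict rests on the text alone; only these frequencies depend on assumed rates. The MTD definition in Section 2.1, the totals of 24 evaluable and 27 enrolled, and the escalation probabilities in Section 9 are sound. The amendment is nevertheless needed, because choosing between the two doses after the data are seen would make that choice post hoc.

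**What to change.** 1. In the last sentence of the Section 4.3 NOTE, replace level 3 by level 4 in both places and state the condition as 0 or 1 DLT in six subjects at that level. If the sponsor does intend 5 mg/kg to go forward even when 10 mg/kg clears, the NOTE should say so, give the reason, and require six subjects at 5 mg/kg.
2. In Section 4.1, change the maximum of 18 evaluable subjects to 24.
3. Minor: add 5 mg/kg to the dose list in Section 1.3.2. State in Section 4.3 that 2 or more DLTs in six at level 1 closes the study with no MTD; the present rule points to a previous level that does not exist there.

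Sections 2.1 and 9 need no change. The cost is a few words in an amendment. Items 1 (as level 4), 2 and 3 need no patients beyond the 24 evaluable and 27 enrolled already planned.

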4.3.1 Definitions

DLT is defined as a significant adverse events (detailed below) occurring during the DLT observation period (consisting of the 2 week pre-induction phase and the 7 weeks of induction phase) that is related to either drug or

NU Study Number: NU 15U06
Merck Study Number: 3475-265

the combination. DLT will be evaluated according to CTCAE v 4.03 criteria. Delay in starting BCG or pembrolizumab therapy by more than 2 weeks due to toxicity during either the pre-induction or induction phases, regardless of attribution or grade, will be considered a DLT.

Significant adverse events qualifying as a DLT are as defined in the table below:

Table 4-3: DLT Definitions			
Local, Bladder-Related Toxicities – Considered to Be DLTs**			
Toxicity	Grade	Including/Requiring	Not Included/Not DLT
Bladder perforation	≥ 2	extra peritoneal perforation	
Bladder spasm	≥ 3	Hospitalization	
Cystitis, noninfective	≥ 3	Transfusion, IV medications, and/or operative intervention	Grade 3 with gross hematuria or requiring elective endoscopic intervention and/or radiologic intervention
Hematuria	≥ 3	Transfusion, operative intervention, limiting self-care ADL	Gross hematuria, IV medication, elective endoscopic procedures, radiologic intervention
Urinary incontinence	≥ 3	Intervention required, limiting self-care ADL	
Urinary retention	≥ 3	Substantial loss of affected kidney function or mass	
Urinary tract obstruction	≥ 3	Symptomatic and altered organ function, endoscopic intervention	
Urinary tract pain	≥ 3	Severe pain, limiting self-care ADL	
Bladder infection	3	Will be DLT only if invasive procedure is required (e.g. draining an abscess).	Antibiotics or other non-invasive procedures required.
	≥ 4	All	
Urinary tract infection	3	Will be DLT only if invasive procedure is required (e.g. draining an abscess).	Antibiotics or other non-invasive procedures required.
	≥ 4	All	
Local, Bladder-Related Toxicities – Will NOT Be DLTs			
Toxicity	Grade	Including/Requiring	Not Included/Not DLT
Urinary frequency	Any	n/a	n/a
Urinary urgency	Any	n/a	n/a
Other, Non-Hematologic Toxicities**			
Toxicity	Grade	DLT or Not?	
All other aside from those listed above.	≥ 3	Will be considered DLT if felt to be related to either drug or the combination, except as noted below.	
Diarrhea	3	Will be considered DLT if refractory to treatment as outlined in Supportive Care Guidelines (Section 4.4.3) Will be considered DLT if lasting >72 hours in the absence of maximal medical therapy	
	4	Bloody or Grade 4 diarrhea will be DLT	
Nausea & vomiting	3	Will only be considered DLT if it is refractory to anti-emetic therapy and unable to be corrected to ≤ Grade 1 within 24 hours. Will be considered DLT if lasting >72 hours in the	

NU Study Number: NU 15U06
Merck Study Number: 3475-265

		absence of maximal medical therapy
Creatinine, elevated	Rise to Grade 3	Will be considered DLT if not corrected to \leq Grade 1 within 24 hours with IV fluids.
Metabolic toxicities (e.g. glucose, hypokalemia, hypomagnesemia, hyperuricemia, hypophosphatemia, and hyponatremia)	\geq 3	Will be considered DLT if unable to be corrected to \leq Grade 2 within 24 hours.
	4 – symptomatic	Will be considered dose-limiting regardless of duration or ability to correct
Drug-induced liver injury	Concurrent AST or ALT $>$ 3x ULN and total bilirubin $>$ 2x ULN	Will be considered DLT. Requires permanent study discontinuation.
Hematologic Toxicities**		
Thrombocytopenia	3 ($<50,000/\mu\text{L}$)	Will be considered DLT if associated with hemorrhage
	4 ($<25,000/\mu\text{L}$)	Will be considered DLT
Neutropenia	4 ($<500/\mu\text{L}$)	Will be considered DLT
	3 ($<1000/\mu\text{L}$) with associated fever (febrile neutropenia)	Will be considered DLT

**Any Grade 2 adverse event lasting greater than 10 days will be considered a DLT.

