1 INTRODUCTION – BACKGROUND & RATIONALE

1.1 Disease Background

In the US, 73,000 patients are diagnosed with bladder cancer each year with 80% of tumors classified as non-muscle-invasive bladder cancer (NMIBC). This group of tumors can be restricted to the bladder mucosa (stage Ta or carcinoma in situ [Tis]) or invade the lamina propria (i.e., subepithelial connective tissue; stage T1). They are optimally treated with curative intent by transurethral resection (TUR). However, approximately 30-80% of these patients will present with tumor recurrences or progression to muscle-invasive disease at five years that contribute to the high prevalence of this malignancy ¹. In 2011, there were an estimated 571,000 people with a history of bladder cancer in the United States ². This wide range of risk of recurrence and progression reflects the biologic heterogeneity of these tumors and the limited risk stratification tools available for the practicing urologist. As a consequence, patients diagnosed with NMIBC are committed to long-term surveillance programs that include office visits, cystoscopies and radiological tests making NMIBC one of the most expensive malignancies to manage ^{3,4}. This elevated risk of recurrence provided the impetus to develop adjuvant treatments following tumor resection with the goals to reduce recurrence and progression to muscle-invasive disease. Adjuvant treatments include intravesical instillation of bacillus Calmette-Guérin (BCG) immunotherapy and intravesical chemotherapy.

Despite adequate induction with 6 weekly instillations with BCG followed by maintenance, 38% of patients still developed recurrence, 7% progressed to muscle-invasive disease, 5% presented distant metastatic disease, and 3% died from bladder cancer ⁵. Although serious adverse effects occurs in <5% of patients, BCG frequently causes cystitis, hematuria, malaise, and fever that results in treatment discontinuation in approximately 20% of patients ⁶. The experience with these side effects might also contribute to the dismal adherence of 40% to cystoscopic surveillance among NMIBC survivors ⁷. These results highlight the need to improve the outcomes and treatment of patients diagnosed with NMIBC.

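### The cystitis and hematuria rows of Table 4-3 conflict for Grade 3 or higher bleeding bladder events, and no rule says which column or term prevails

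*Combined protocol and SAP*

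**What the plan says.** Section 4.3.1 of the protocol states that "DLT will be evaluated according to CTCAE v 4.03 criteria" and sets out the qualifying events in Table 4-3. Each local toxicity has a grade, a column of features that make it a DLT, and a column of features that do not. Two rows matter here, both starting at Grade 3.

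- **Cystitis, noninfective.** Counts as a DLT: "Transfusion, IV medications, and/or operative intervention". Does not count: "Grade 3 with gross hematuria or requiring elective endoscopic intervention and/or radiologic intervention".
- **Hematuria.** Counts as a DLT: "Transfusion, operative intervention, limiting self-care ADL". Does not count: "Gross hematuria, IV medication, elective endoscopic procedures, radiologic intervention".

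Two general rules sit beside the table. "Delay in starting BCG or pembrolizumab therapy by more than 2 weeks due to toxicity" is a DLT whatever its grade or attribution. The table footnote adds: "Any Grade 2 adverse event lasting greater than 10 days will be considered a DLT".

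Section 2.1 defines the maximum tolerated dose (MTD) from the DLT count, and Section 4.3 gives the 3+3 rules. Zero of 3 escalates, 1 of 3 expands to 6, 1 of 6 escalates, and 2 or more stops. The Data Monitoring Committee reviews toxicity data before each escalation. Section 1.1 says that "BCG frequently causes cystitis, hematuria, malaise, and fever".

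**The concern.** Bladder inflammation with bleeding can reasonably be recorded as cystitis, as hematuria, or as both; Section 4.4 lists both among the local toxicities of treatment. For such an event the table does not give one answer. The two rows treat IV medication in opposite ways, and within each row a bleeding event can satisfy the DLT column and the exempt column together. Sections 4.3.1, 4.4 and 9 contain no precedence rule, no rule for choosing the term, and no classification rule for the committee.

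The DLT count is the only input to the MTD. With 3 to 6 patients per level, one patient scored differently can turn escalation into expansion or a stop. At level 1, moving from 1 of 3 to 2 of 3 closes the study.

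**Working it through.** **Step 1. The rows side by side.**

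| Feature | Cystitis row | Hematuria row |
|---|---|---|
| Transfusion, operative intervention | DLT | DLT |
| IV medication | DLT | Not DLT |
| Limiting self-care ADL | Not mentioned | DLT |
| Gross hematuria | Not DLT | Not DLT |
| Grade limit on the exemption | Grade 3 only | None |

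**Step 2. Try each possible order of precedence.**

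*Rule A: the DLT column prevails.*
- Grade 3, gross hematuria, IV medication only: a DLT under cystitis, not a DLT under hematuria.
- Grade 3, gross hematuria, limiting self-care ADL only: a DLT under hematuria. The cystitis row lists no qualifying feature for it, but does not name ADL as exempt either.
- Gross hematuria with transfusion: a DLT under both.

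*Rule B: the not-DLT column prevails.*
- Grade 3 with gross hematuria: exempt under both terms, even with transfusion. For bleeding events this removes most of what the DLT column was written to catch.
- Grade 4 with gross hematuria and transfusion: a DLT under cystitis, whose exemption stops at Grade 3; exempt under hematuria, whose exemption has no grade limit.

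Under either rule at least one event is scored differently by term. A precedence sentence alone is therefore not enough; the rows must also be made to agree.

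**Step 3. Reproduce the plan's figures.** Section 9 gives a 91%, 49% and 17% chance of escalating at true DLT rates of 10%, 30% and 50%. With DLT probability p per patient,

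P(escalate) = (1−p)³ + 3p(1−p)² × (1−p)³

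- p = 0.10: 0.729 + 0.243 × 0.729 = 0.906
- p = 0.30: 0.343 + 0.441 × 0.343 = 0.494
- p = 0.50: 0.125 + 0.375 × 0.125 = 0.172

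These agree with the plan, so its arithmetic is not in question.

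**Step 4. Illustrate the sensitivity.** Assumptions, none from the documents: unambiguous DLTs occur in b = 10% of patients, and ambiguous events occur in a further, separate q. The comparison is p = b (ambiguous events exempt) against p = b + q (counted).

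| q | P(escalate), exempt | P(escalate), counted | Difference |
|---|---|---|---|
| 1% | 0.906 | 0.705 + 0.261 × 0.705 = 0.889 | 1.7 points |
| 2% | 0.906 | 0.681 + 0.279 × 0.681 = 0.871 | 3.5 points |
| 5% | 0.906 | 0.614 + 0.325 × 0.614 = 0.814 | 9.2 points |
| 10% | 0.906 | 0.512 + 0.384 × 0.512 = 0.709 | 19.8 points |

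Counting more events can only turn an escalation into a non-escalation, so the difference is also the share of cohorts in which the same patients would lead to opposite decisions. Full enumeration of six-patient outcomes confirms this at q = 5% and 10% (0.092 and 0.198). The comparison is between all ambiguous events scored one way and all scored the other, so it is the widest gap for each q.

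**The case against.** **A sensible reader would count transfusion.** The natural reading is that gross hematuria by itself does not qualify, while transfusion or an operation does. Rule B is hard to defend because it empties much of the DLT column. This has force, and it makes the overlap within a row the weaker half of the point. But the table does not say it, and that reading is Rule A, under which the IV-medication conflict remains.

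**Term dependence is conditional.** A reader might infer that bleeding cystitis needing IV medication is always a DLT under one term and never under the other. That holds only if the DLT column prevails; under Rule B, Grade 3 events of this kind are exempt in both rows. Nor is self-care ADL a mirror-image conflict: it is absent from the cystitis row, not excluded, and the separate urinary tract pain row can capture painful cases.

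**Both terms could be recorded.** Nothing forbids this, and an exempt hematuria entry need not cancel a qualifying cystitis entry. But neither dual recording nor its scoring is specified.

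**Other rules and reviews act as safeguards.** A toxicity delay of more than 2 weeks is a DLT in any case, and a Grade 2 event lasting more than 10 days is too. These narrow the gap. They do not close it, because Section 4.4 allows treatment to be held for up to 14 days and then resumed, so a short-lived Grade 3 event need not trigger either. The committee reviews toxicity but has no classification rule to apply. The trial is single-center, so variation in coding between sites is not the issue; consistency between patients and cohorts is.

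**The event rate is unknown.** This stands. Section 1.1 reports serious adverse effects of BCG in fewer than 5% of patients. That figure is for BCG alone, and serious is not the same as Grade 3 or higher, but it lends no support to large values of q.

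**Conclusion.** The contradiction is real and rests on the table alone: the two rows give opposite answers on IV medication, both columns can be met at once, and no order of precedence makes the rows agree. Because the DLT count alone determines the MTD, it should be corrected even though the affected events are a narrow class. They are Grade 3 or higher cystitis or hematuria with the listed features, resolving soon enough to avoid the other DLT rules.

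The effect on escalation cannot be stated from the documents. Under the assumed 10% base rate it runs from about 2 points (q = 1%) to about 20 points (q = 10%).

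Two stronger conclusions are tempting and not supported. One is that the primary endpoint is indeterminate in general; most DLT definitions are unaffected. The other is that this is the most expected local toxicity. Section 1.1 calls cystitis and hematuria frequent with BCG, without ranking or grade-specific rates, and urgency and frequency, which the protocol also anticipates, are explicitly never DLTs.

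**What to change.** Amend Table 4-3 to do three things:

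1. Reconcile the cystitis and hematuria rows on IV medication, self-care ADL and the grade limit of the exemption.
2. State which column prevails when an event meets both.
3. State that an event fitting both terms is scored once, and the same way whichever term is coded.

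Which events should count is for the sponsor and investigators to decide. Then re-check Grade 3 or higher local events in completed cohorts against the reconciled table.

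The cost is table wording in an amendment and a short data review. The downside is that a past event may change classification, and with it a past escalation decision.
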